Airway clearance is a strategy for treating symptoms of respiratory disorders by improving a patient's respiratory status by enhancing mucus clearance, reducing airway resistance, enhancing gas exchange, and reducing overall work of breathing. Chest physiotherapy and airway clearance has been the mainstay of treatment and prevention of exacerbation in the cystic fibrosis (CF) population for decades, and has had its use expanded to the non-CF bronchiectasis and acute bronchiolitis populations, and in patients being mechanically ventilated. There have also been recent positive trials within the realm of chronic bronchitis and COPD as well which showed that airway clearance was beneficial in reducing the daily volume of sputum produced and increasing FEV₁.

There have been several small studies done to analyze the utility of airway clearance and its potential role in CAP. These studies have generally been small and have used a wide variety of airway clearance devices and techniques, including external chest wall physiotherapy devices and postural drainage, both now considered second line therapies for most patients. These studies have been variable in their findings and overall have not shown that airway clearance is either beneficial or harmful in CAP. The studies did show, however, that the duration of fever and hospital length of stay were both significantly decreased, suggesting the possibility of other clinically important benefits.(Ntoumenopoulos 2002; Tydeman 1989).

Objectives:

We will test our hypothesis that the use of oPEP devices, specifically the handheld Aerobika (Monaghan Medical) in this study, will result in more rapid and durable recovery in patients hospitalized with community-acquired pneumonia as measured by decreased hospital length of stay, reduced duration of fever, improvement in dyspnea, decreased duration of antibiotics, increased rate of diagnosis of the etiologic organism responsible for the pneumonia, and reduced readmission rates:

Primary outcome

1. Reduction in hospital length of stay

Secondary outcomes

1. Reduction in dyspnea by modified-Borg score
2. Reduction in duration of antibiotics
3. Reduction in duration of fever
4. Reduction in need for oxygen at hospital discharge
5. Reduction in 30-, 60-, and 90-day readmission rates
6. Diagnosis of organism by sputum
7. Transfer to the intensive care unit (ICU)

Study type: Prospective randomized controlled trial**Design:**

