The study investigators will perform daily screening by chart review of patients admitted to the hospital in the previous 24 hours using the ICD-10 codes as below to find appropriate patients for secondary screening:

J13 Pneumonia due to Streptococcus pneumoniae

J14 Pneumonia due to Hemophilus influenzae

J15 Bacterial pneumonia, not elsewhere classified

J16 Pneumonia due to other infectious organisms, not elsewhere classified

J17 Pneumonia in diseases classified elsewhere

J18 Pneumonia, unspecified organism

J69 Pneumonitis due to inhalation of food and vomit

A partial HIPAA waiver will be obtained for the purposes of focused screening for eligibility. If the patient is deemed eligible for the study, the study investigators will approach the hospitalist/teaching attending for collateral information and permission to approach the patient for consent. After consent is obtained, the study investigator will perform a brief patient interview to obtain information on race/ethnicity, smoking and alcohol history, to confirm past medical and medication histories, and to perform baseline assessments of dyspnea (modified BORG).

Once consent is obtained, Patients will then be randomized using block randomization. We will receive pre-made envelopes in blocks of 10 from a centralized research coordinator. Investigators performing the initial screening and enrollment will be blinded to the envelope contents until after the patient consents to participation in the study. Once the patient consents to participation, the next consecutively numbered envelope will be opened revealing the allocation to either the control or intervention group. The principal investigator will keep the envelopes secured, and will be responsible for providing each envelope to the enrolling investigator after consent has been obtained.

The intervention will consist of oPEP therapy added to standard pneumonia care (see below). "Standard pneumonia care" will not be dictated by the study protocol, but rather at the discretion of the treating clinicians. Patients who are initially admitted to the intensive care unit (ICU) will not be included in this study even when they are downgraded to general medical floors, but patients will not be excluded if they are enrolled while on the medical floors and are later upgraded to ICU level of care. Enrollment will occur Monday through Friday, thus including patients being admitted on Sunday through Friday.

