Patients in the intervention group will be directed to perform the Aerobika therapy twice daily under the guidance of a study investigator for a total of at least 5 minutes per session. The study investigator will appropriately adjust the device on first use, as well as teaching the patient the correct technique for device usage. The primary patient-centered outcome will be the modified-Borg score for dyspnea which will be collected on admission, and on each subsequent morning until discharge on all enrolled patients. Patients will be encouraged to use the device on their own between the monitored sessions, as the device can safely be used multiple times daily. Patients will be surveyed each morning to self-report additional usage of the device. The device will also be available in the patient's room for in-line use of nebulizer treatments

administered by respiratory therapists, at the discretion of the therapist. Ordering of any nebulized medications is at the discretion of the treating clinicians or respiratory therapists, the latter through a standard and general respiratory therapist-driven protocol used in our institution. Charting of any nebulizer therapy will be reviewed to assess additional use of the device as well. The intervention will continue through the duration of the patient's hospitalization, and the patient will have the option to take the device at home with them if they wish to continue using it after discharge. If patients experience intolerable dyspnea or chest tightness during use of the Aerobika, despite coaching and troubleshooting by the bedside investigator, the Aerobika session will be aborted. If the patient is unable to tolerate the therapy during three consecutive sessions, then the patient will be withdrawn from intervention.

Crossover into the Aerobika group will not be restricted if the attending physician treating the patient deems it a necessary part of the patient's care. Rates of crossover will be collected as part of study data. All analyses will be performed using intention-to-treat as well as a modified intention-to-treat method considering the intervention group to include patients randomized to intervention AND who received at least one Aerobika treatment.

Variables to be collected

Demographics: Age at admission Gender Race/ethnicity (self-reported)	Lifestyle: Smoking history (ever/current/never) Alcohol consumption frequency

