Home and inpatient medications: PPI/H2-blockers Statins? Hypoglycemics/insulin Systemic steroids Inhaled medications including by nebulization Immunosuppressives	Symptoms:

Physical/Vital signs: BMI (height/weight at admission) Heart rate (daily maximum/minimum) Pulse oximetry (daily maximum/minimum, including FiO2 maximum/minimum) Temperature (daily maximum/minimum) Blood pressure (daily maximum/minimum)	Comorbidities/Past Medical History : CVA Heart disease Renal failure Cancer, active in last 6 months or not (excluding non-melanoma skin cancers) Lung disease (ie. asthma, COPD, ILD, bronchiectasis) GERD Oropharyngeal or other dysphagia
Scores: PSI - pneumonia severity index CURB65 Subjective (cough, dyspnea, mucus production) Modified-Borg score for dyspnea	

Sample size calculations

The median hospital length of stay (LOS) for Norwalk Hospital based on FY2017 data was 4.6 days (SD 3.16 days) for patients coded with a primary diagnosis of pneumonia. We will employ an effect size of 25%, powering for a reduction in LOS by 1 day.

**Two independent study groups
The primary endpoint is an average LOS (continuous variable).**

Sample Size
 Group 1 119
 Group 2 119
 Total 238

Study Parameters
 Mean LOS, group 1 4.6
 Mean LOS, group 2 3.45

Patient identity will be protected through the use of the EHR, as well as by saving abstracted PHI on a password-protected, data-encrypted, secured drive managed by information

technology (IT) at Norwalk Hospital. Additional considerations include the use of REDCap, a secured research platform, for primary data collection and storage. Data will be destroyed when all analyses and publications have been completed.

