Risks to patients are negligible as the intervention device is a safe, drug-free, easy to use, and non-invasive. Our exclusion criteria are focused on eliminating any individuals who would be at increased risk of adverse events from using an oPEP device, although such events are very rare. With any airway clearance modality there is the possibility of transient mild bronchospasm and hypoxemia at the initiation of the clearance which improves once the mucus is expectorated. This subtle physiologic phenomenon is typically not clinically evident nor of clinical significance, but this can be ameliorated with coaching by respiratory therapists and investigators who are all trained in the appropriate use of this device, and who are also highly trained to provide immediate care if any clinically evident events occur. The respiratory therapists are very familiar and comfortable with the Aerobika as they are currently using it with patients at Norwalk Hospital for augmentation of secretion clearance, typically in the context of bronchiectasis or COPD exacerbations.

Participation in this study should not result in any additional costs to the patient.

Potential benefits to patients include improved mucociliary clearance, reduction in length of hospitalization, duration of fever, improvement in respiratory symptom-related quality of life and duration of antibiotics, all of which have been shown to be statistically significant in previous studies, although not specific to inpatient treatment of pneumonia, as this study aims to do.

Selection and withdrawal of subjects:

Our inclusion and exclusion criteria are developed based on existing literature, the manufacturer's FDA approval, and the scope of our study.

Inclusion

1. Age 18 years or older
2. Clinical symptoms suggesting pneumonia (eg. cough, fever, pleuritic chest pain, sputum production, dyspnea)
3. Any new chest radiographic infiltrate consistent with pneumonia

Exclusion

1. Untreated or recently (within the past 90 days) treated pneumothorax
2. Active hemoptysis
3. Recent facial, oral, or skull trauma
4. Hemodynamically unstable patients
5. Severe nausea or active vomiting
6. Recent diagnosis of pneumonia prior to current inpatient encounter (within 60 days)
7. Significant cognitive impairment or psychiatric conditions that prevent ability to participate in or cooperate with oPEP use
8. Active tuberculosis or negative pressure isolation for rule out of active tuberculosis
9. Pregnancy

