10. Pre-existing medical condition with a life expectancy of less than 3 months
11. Inability to form appropriate mouth seal on device (eg. due to neuromuscular disease)
12. Pre-existing active use of oPEP devices
13. Requiring $\geq 50\%$ FiO₂ or facemask (excluding high flow NC)

Assessment of Efficacy:

This study is not designed to assess the efficacy of any drug, supplement, device, etc.

Assessment of Safety:

No known safety issues exist as no procedures will be conducted on patients for this study outside of the scope of their current use. Furthermore all medical devices in this study are FDA approved and currently being used for the indication being studied in this project.

Statistical Analysis:

Comparative statistics will be employed to determine if outcomes in the intervention (oPEP) group are statistically different from those in the control group. This will be done with the assistance of in-network statisticians as well as available statistical software.

Direct Access to Source Data Documents:

The study's Principal Investigator, primary study coordinator, and co-investigators will have access to all study data. These data will be used for study purposes only, and will be stored on a password-protected, data-encrypted, secure drive managed by IT at Norwalk Hospital. Data may be released to regulatory agencies as necessary, including the US Food and Drug

Administration, Department of Health and Human Services agencies, BRANY, the WCHN IRB, accrediting agencies, and data safety monitoring boards.

References:

2. Diana Tydeman (1989) An investigation into the effectiveness of physiotherapy in the treatment of patients with community-acquired pneumonia, *Physiotherapy Practice*, 5:2, 75-81, DOI: 10.3109/09593988909044416

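### Does the missing rule for in-hospital deaths in length of stay and readmission call for a change to the plan?

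*Combined protocol and SAP*

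**What the plan says.** The Objectives make reduced hospital LOS the primary outcome. The Sample size calculations section treats it as a mean: "The primary endpoint is an average LOS (continuous variable". The seven secondary outcomes include "Reduction in 30-, 60-, and 90-day readmission rates" and "Transfer to the intensive care unit (ICU"; death is not among them.

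The Design section fixes who is analysed: "All analyses will be performed using intention-to-treat as well as a modified intention-to-treat method". It also keeps patients who deteriorate: "patients will not be excluded if they are enrolled while on the medical floors and are later upgraded to ICU level of care". The Statistical Analysis section promises comparative statistics without naming a method, and Assessment of Safety plans no tabulation of deaths.

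Several criteria remove the patients most likely to die. Under Design: "Patients who are initially admitted to the intensive care unit (ICU) will not be included in this study". Among the exclusions are "Hemodynamically unstable patients", "Pre-existing medical condition with a life expectancy of less than 3 months", and a need for at least 50% inspired oxygen or a facemask.

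**The concern.** Death ends a hospital stay without recovery. If observed stays are averaged, an early death looks like a quick discharge and a late death like a slow one. A mortality difference between the arms would then move the primary result in a direction set by the timing of the deaths. Patients who die also cannot be readmitted, so keeping them in the denominator lowers the readmission rate.

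Intention-to-treat says who is counted, not the value a death takes. Counting the stay to the day of death, omitting the patient, censoring and ranking death worst are all unaddressed, so the rule could be picked after results are known. With no planned count of deaths by arm, a reader could not tell whether a shorter mean LOS reflected faster recovery or earlier death. For a trial meant to show faster and more lasting recovery, that matters in principle.

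**Working it through.** **Inputs from the plan.** Sample size calculations: mean LOS 4.6 and 3.45 days, SD 3.16, 119 per group (4.6 is called a median in the text and a mean in the parameter list; it is used here as a mean). Background: local 30-day readmission 13.1%.

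**Assumptions.** Deaths (control versus oPEP) of 2% v 3%, 2% v 5% and 5% v 10%; death at day 2 or day 8; two-sided 5% test and 80% power, neither stated in the plan.

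**1. The plan's own figure.** n = 2 × (1.960 + 0.842)² × 3.16² / 1.15² = 2 × 7.849 × 9.986 / 1.3225 = 118.5, so 119 per group. This matches and contains no allowance for deaths.

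**2. Yardstick.** Standard error of the difference = 3.16 × √(2/119) = 0.41 day.

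**3. Observed stay averaged, survivors at 4.6 days in both arms.** Arm mean = (1 − p) × 4.6 + p × d, so the shift (oPEP minus control) = (p₁ − p₀) × (d − 4.6).

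| Deaths | Day 2 | Day 8 | Share of 1.15 | In standard errors |
|---|---|---|---|---|
| 2% v 3% | −0.026 | +0.034 | 2.3%, 3.0% | 0.06, 0.08 |
| 2% v 5% | −0.078 | +0.102 | 6.8%, 8.9% | 0.19, 0.25 |
| 5% v 10% | −0.130 | +0.170 | 11.3%, 14.8% | 0.32, 0.41 |

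Death at day 4.6 gives no shift.

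**4. Effect on the test.** With gamma and lognormal stays, at least 20,000 runs per scenario, no effect in survivors and deaths at day 2, simulated false benefit (nominal 2.5%) is 2.8-3.0%, 3.7-4.0% and 4.7-5.2% for the three rows. With deaths at day 8 the error is false harm: 3.1%, 4.1-4.6% and 6.1-6.3%. That counts against oPEP in scenarios where oPEP does have more deaths.

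**5. Equal mortality.** With no LOS effect and the same timing of death, the shift is zero; simulated false benefit at 2% or 5% deaths per arm is 2.4-2.7%. With a true 1.15-day effect in survivors, equal deaths dilute it: at 5% per arm, 0.95 × 1.15 = 1.09 days, a loss of 0.06 day. That is conservative.

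**6. Deaths left out instead.** If death is unrelated to stay, the shift is zero. If the risk of death is proportional to the stay the patient would have had, those who die have mean stay 4.6 + 3.16²/4.6 = 6.77 days, and the survivor mean is (4.6 − p × 6.77)/(1 − p). The differences are −0.023, −0.070 and −0.127 day, no larger than the day-2 shifts in step 3.

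**7. Readmission.** Take 13.1% among patients discharged alive and keep deaths in the denominator. The change between arms is 119 × 0.131 × (p₁ − p₀) = 0.16, 0.47 and 0.78 patient.

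**The case for a change.** The strongest case for a change has three parts.

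*Deaths will occur.* At an assumed 2%, 238 × 0.02 = 4.8 deaths are expected, and the chance of at least one is 1 − 0.98²³⁸ = 99%. Some rule will be needed. This stands.

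*The rule matters even with equal mortality.* At 2% deaths per arm, power is 79.4% with survivors only, 73% if each death is assigned 14 days and 45% if assigned 30 days. The arithmetic is right, but nothing in the plan supports an assigned value. The endpoint is a plain average; its benchmark is hospital data for patients coded with pneumonia, with no stated restriction to survivors; and all analyses include intention-to-treat. Observed stay for everyone randomised is the direct reading, although it remains an inference.

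*Deaths by arm would stay hidden, and showing them costs almost nothing.* This is the best part. Abstracting LOS and oxygen need at discharge already means reading how each admission ended, so the count is at hand and belongs beside the LOS result. It is a matter of reporting and does not alter the planned comparison.

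Heavier remedies gain little. Accepting a shorter mean LOS as benefit only when an analysis ranking deaths worst agrees in direction leaves false benefit essentially unchanged in the first two scenarios and lowers it only to 3.9-4.4% in the third. Restricting readmission to patients discharged alive selects on a post-randomisation event, sits uneasily with intention-to-treat, and still ignores deaths after discharge that prevent readmission.

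**Conclusion.** The gap is real, but it is missing detail that a competent analyst would fill with observed stay in all randomised patients. Under that rule the LOS comparison is valid when mortality is equal. A difference of one percentage point moves it by about 0.03 day, under a tenth of a standard error. A noticeable distortion (0.13 to 0.17 day) needs oPEP to double mortality from 5% to 10%, for which the documents give no support. The readmission effect is below one patient per arm in every scenario.

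This rests on trial mortality being well below the Background's upper figure of 16%. That is reasonable given the exclusions but is not documented, and the death rates and days used are assumptions. Writing the rule down and showing deaths by arm, including those after discharge that precede any readmission, would be good reporting practice. Neither alters the endpoint, the sample size or the likely conclusion, so no change to the plan is called for.

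### Exclusion 11 (mouth seal on the device) has no described check before randomization, so cases not evident from the chart or at the bedside surface almost only in the device arm

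*Combined protocol and SAP*

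**What the plan says.** The exclusion list under Selection and withdrawal of subjects contains, as item 11, "Inability to form appropriate mouth seal on device (eg. due to neuromuscular disease". Neuromuscular disease is given only as an example; the criterion itself is functional and refers to the device.

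The Design section gives the order of steps:

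- Screening: "The study investigators will perform daily screening by chart review of patients admitted to the hospital in the previous 24 hours". This finds candidates for a secondary screening whose content is not described.
- A patient judged eligible is discussed with the attending physician, whose permission is needed before the patient is approached for consent.
- After consent, "the study investigator will perform a brief patient interview to obtain information on race/ethnicity, smoking and alcohol history". The interview also confirms medical and medication histories and takes the baseline modified Borg score.
- Randomization: "Once the patient consents to participation, the next consecutively numbered envelope will be opened revealing the allocation to either the control or intervention group".
- Treatment: "Patients in the intervention group will be directed to perform the Aerobika therapy twice daily under the guidance of a study investigator". In the same paragraph: "The study investigator will appropriately adjust the device on first use, as well as teaching the patient the correct technique for device usage".

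The Design section then plans every analysis twice, by ITT and by a modified ITT (mITT), the latter "considering the intervention group to include patients randomized to intervention AND who received at least one Aerobika treatment". It sets no matching condition for controls and does not say which analysis is primary. Crossover to the device is allowed when the attending physician considers it necessary. The only withdrawal rule concerns sessions that are not tolerated, and it withdraws the patient from the intervention, not from the study.

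**The concern.** An eligibility criterion should be settled for every patient before allocation is known, by the same means in both arms. Here no step listed before the envelope puts a mouthpiece to the patient's lips. Some causes of seal failure will be known from the chart or seen at the bedside, and those are caught equally in both arms. The remainder come to light at first use, which follows allocation and takes place in the intervention group. Their counterparts among the controls are not identified unless they happen to cross over.

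Two consequences follow, one for each planned analysis. If these patients stay in the device arm, they are counted as treated but receive little or no treatment, and the estimated effect shrinks. If they never receive a treatment and so fall outside the mITT set, the device arm loses them while the control arm keeps its own. If such patients tend to be weaker and stay longer, the comparison then favours the device even when it does nothing.

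**Working it through.** **Inputs from the protocol (Sample size calculations):** mean LOS 4.6 and 3.45 days, a difference of 1.15 days; SD 3.16 days; 119 per group.

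**Assumptions:**

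- Two-sided alpha 0.05 and power 0.80 are not stated in the text; they are adopted because they reproduce the sample size.
- f is the share of randomized patients with a seal failure not recognised before allocation: 2%, 5% or 10%.
- D is how much longer those patients stay than the rest: 1, 2 or 3 days.
- The documents give no figure for f or D.

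**Step 1, the plan's own figure.** n per group = 2 × (1.960 + 0.842)² × 3.16² / 1.15² = 118.5, rounded up to 119. The stated figure is reproduced. Power at 119 per group is 0.802. (A difference of exactly 1.0 day, also mentioned in that section, would need 157 per group, so 1.15 is the value behind the stated size.)

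**Step 2, ITT.** If unrecognised non-sealers get no effect from the device, the expected difference is 1.15 × (1 − f). The standard error is 3.16 × √(2/119) = 0.410, and power = Φ(difference/0.410 − 1.960). For f = 5%: 1.15 × 0.95 = 1.09 days, power 0.76.

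**Step 3, mITT.** Let the other patients have mean LOS m. With no device effect, the full control arm has mean m + f × D. If all non-sealers drop out of the device arm, that arm has mean m. The false benefit is f × D. Two-sided type I error is Φ(b/se − 1.960) + Φ(−b/se − 1.960), with b = f × D and se = 3.16 × √(1/119 + 1/(119(1 − f))). For f = 5%, D = 2: b = 0.10, se = 0.415, type I error 5.7%.

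| f | Device patients (of 119) | ITT difference (days) | ITT power | mITT false benefit at D = 1, 2, 3 (days) | Share of 1.15 days | mITT type I error at D = 1, 2, 3 |
|---|---|---|---|---|---|---|
| 2% | 2.4 | 1.13 | 0.79 | 0.02, 0.04, 0.06 | 2%, 3%, 5% | 5.0%, 5.1%, 5.2% |
| 5% | 6.0 | 1.09 | 0.76 | 0.05, 0.10, 0.15 | 4%, 9%, 13% | 5.2%, 5.7%, 6.5% |
| 10% | 11.9 | 1.04 | 0.71 | 0.10, 0.20, 0.30 | 9%, 17%, 26% | 5.7%, 7.6%, 11.0% |

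The mITT columns assume that every unrecognised non-sealer receives no treatment at all, so they are upper values for each f and D.

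**The case against.** The strongest reply is that ITT is already planned. Nothing in the protocol permits removing a randomized patient as ineligible, and the withdrawal rule stops only the intervention. A reader might infer that seal failures will be struck from the device arm and that the primary comparison is therefore biased. The documents do not support that. Under ITT as written these patients stay where they were randomized, and the cost is dilution, not bias. This stands, and it confines the bias to the mITT set. Even there removal is possible rather than certain, because the protocol does not define whether a failed first attempt counts as a treatment.

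A reader might also extend the point to exclusion 7, which ends "prevent ability to participate in or cooperate with oPEP use". That does not follow. The criterion is limited to significant cognitive impairment or psychiatric conditions, which chart review, the attending physician, the consent discussion and the interview can reveal in both arms without the device.

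Three further replies stand in part:

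- The absence of a seal check is read from silence. The secondary screening is not described, and the investigator meets every patient before the envelope is opened. Obvious cases would probably be noticed, and the exclusion for recent facial or oral trauma catches some others. This lowers f but does not make the check equal in both arms.
- Crossover means that some controls may try the device, so discovery is nearly, not strictly, confined to one arm.
- f and D are assumed. At f = 2% and D = 1 the effect is negligible.

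**Conclusion.** The point holds as a gap in the order of steps. Exclusion 11 refers to performance on the device, and the only described first use comes after allocation in the intervention group. The stated sample size leaves almost no spare power (0.802 at 119 per group), so ITT dilution costs about 2 to 9 percentage points over the assumed range. The mITT set is the one written route to one-sided loss, with a false benefit of at most 2% to 26% of the planned difference. Both ranges rest on assumed f and D, and the true size cannot be established from the documents; it is probably small unless unrecognised seal failure is common. The documents do not show that the ITT result is biased. The case for change is that a near-costless step would apply the plan's own criterion equally to both arms.

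**What to change.** In the Design section, add a step after consent and before the envelope is opened: in every consenting patient, the enrolling investigator checks the mouth seal on a disposable mouthpiece, ideally the device's own, without giving therapy. Patients who fail are recorded as screen failures and no envelope is opened for them.

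State that no patient is removed from the study or the analysis under exclusion 11 once the envelope has been opened. Name ITT as the primary analysis and mITT as supportive.

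The cost is about a minute within the existing bedside interview, one mouthpiece per patient, and a few consented patients who become screen failures. The check is not complete: a seal that fails only against expiratory resistance may still appear after allocation. That is why the rule against later removal and the choice of ITT as primary are needed alongside it.

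### The protocol names possible device effects and has intolerance rules but plans no adverse-event recording, so session-level harms would not be captured systematically and only indirect measures could be compared by arm.

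*Combined protocol and SAP*

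**What the plan says.** The Assessment of Safety section is two sentences long. The first reads "No known safety issues exist as no procedures will be conducted on patients for this study outside of the scope of their current use". The second adds: "Furthermore all medical devices in this study are FDA approved and currently being used for the indication being studied in this project". It does not define an adverse event, and it plans no recording, grading, attribution or tabulation.

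Three other places bear on this.

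- The risk paragraphs, which stand before the selection criteria, say: "With any airway clearance modality there is the possibility of transient mild bronchospasm and hypoxemia at the initiation of the clearance". They then qualify this: "This subtle physiologic phenomenon is typically not clinically evident nor of clinical significance". They call adverse events very rare but give no rate. They describe present use of the device at the hospital as "typically in the context of bronchiectasis or COPD exacerbations".
- The Design section provides for intolerance. The rule that opens "If patients experience intolerable dyspnea or chest tightness during use of the Aerobika" ends in aborting the session if coaching does not help. Three untolerated sessions in a row lead to withdrawal from the intervention.
- The Objectives and the variable list include measures that bear on harm: daily extremes of pulse oximetry with FiO2, heart rate and blood pressure; oxygen need at discharge; ICU transfer; and readmission at 30, 60 and 90 days. The Design section adds a modified Borg score every morning in all enrolled patients.

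**The concern.** A safety section that declares no issue removes the reason to collect anything, and this one collects nothing. The rest of the protocol does not treat the device as free of effects: it names two and makes provision for patients who cannot tolerate it. The Background also reports that earlier airway-clearance studies in community-acquired pneumonia showed neither benefit nor harm overall, so harm in this population is an open question by the protocol's own account. Patients on supplemental oxygen below the 50% FiO2 exclusion limit can be enrolled, so hypoxemia is relevant to them.

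At stake is what the trial can say about tolerability. Daily chart values can be retrieved later. An aborted session, its reason, or wheeze during a session cannot be recovered at analysis unless someone wrote it down at the time. A report of shorter stay would then carry no reliable count of how often the device was not tolerated.

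**Working it through.** **What each named or implied harm would leave in the data**

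| Event | Where the protocol raises it | Planned capture |
|---|---|---|
| Bronchospasm | Risk paragraphs | None stated |
| Hypoxemia at the start of clearance | Risk paragraphs | Indirect: daily minimum SpO2 with FiO2 |
| Intolerable dyspnea or chest tightness, session aborted | Design | None stated; morning Borg is indirect |
| Withdrawal from the intervention for intolerance | Design | None stated |
| ICU transfer | Objectives, secondary outcome 7 | Collected in both arms |
| Readmission | Objectives, secondary outcome 5 | Collected in both arms |
| Death in hospital | Background gives case fatality up to 16% | Not a listed outcome |

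The Design section does say that crossover rates will be collected and that patients will be surveyed each morning about extra device use. It says nothing similar about aborted sessions or intolerance. The section on access to source data names regulators and safety monitoring boards as possible recipients of data, but sets up no board and no event reporting.

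**Timing.** The named effects occur at the start of clearance and are described as transient. Sessions are supervised twice daily. One daily minimum SpO2 and one morning Borg score are not linked to a session, so a short fall or a brief episode of dyspnea can go unseen. If it is seen, it cannot be assigned to the device.

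**Number exposed.** Inputs from the sample size section: means 4.6 and 3.45 days, so a difference of 1.15; SD 3.16. Alpha and power are not stated; I assume two-sided 0.05 and 80%.

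n per arm = 2 × (1.960 + 0.842)² × 3.16² / 1.15² = 118.5, rounded up to 119. This matches the stated 119 per arm (238 in total).

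**What 119 recorded patients could show (illustration only, since no event rate is given)**

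- Zero events recorded: one-sided 95% upper limit = 1 − 0.05^(1/119) = 0.0249, or 2.5%.
- Chance of at least one event = 1 − (1 − p)^119: 11% at p = 0.1%, 70% at 1%, 91% at 2% and 99.8% at 5%.

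These figures assume that all 119 patients in the device arm use the device and that every event is recorded. They describe one arm, not a comparison, and do not estimate harm.

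**The case against.** The strongest reply is that the trial does collect data on harm. A reader might infer from the safety section that there are no safety data and that harm cannot be compared by arm. The documents do not support that. Oximetry, Borg, ICU transfer and readmission are collected in both arms, and the Statistical Analysis section compares outcomes without fixing a direction. ICU transfer is listed without the word reduction, so an excess in the device arm would be visible. This part of the reply stands; what remains is the session-level gap.

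Two other inferences also go too far.

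- That intolerant patients vanish from the analysis. They are withdrawn from the intervention, not from the study, and an intention-to-treat analysis is planned, so their outcomes stay in. Applying the withdrawal rule also implies some tracking of tolerance. What is not stated is that intolerance will be recorded and reported.
- That the device is not used for pneumonia at this hospital. The risk paragraph says only that use is *typically* in other conditions, and the indication in the safety section may mean secretion clearance in general. Set beside "currently being used for the indication being studied in this project", this is an ambiguity to reconcile, not a proven contradiction.

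It is also fair to say that the protocol calls the effects mild, aims its exclusions at patients at raised device risk, and has trained staff on hand. These points lower the expected risk. They do not supply a record of what happened.

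**Conclusion.** The point holds in a limited form. The statement that no safety issues are known does not fit the protocol's own list of possible effects and its intolerance rules. There is no plan to record device-related events, aborted sessions or intolerance withdrawals. Comparison by arm is possible only through indirect measures that are not tied to sessions and could miss transient effects.

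The size cannot be computed from the documents, which give no event rate. The 2.5% limit shows only what systematic recording in 119 device patients could offer if no event occurred; without recording, that reassurance is not available for session-level events. The conclusion assumes that no separate safety procedure or case report form outside these documents fills the gap. The change is worth making because it is cheap and the information cannot be recovered later. The primary length-of-stay analysis does not depend on it.

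**What to change.** Replace the safety statement with a short plan that changes measurement and reporting only.

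1. At each supervised session, the investigator already present records whether the session was aborted and why, and any clinically evident bronchospasm or desaturation.
2. The existing morning survey of device use also asks about problems during unsupervised use.
3. Aborted sessions, device-related events and intolerance withdrawals are reported as rates among all device-exposed patients, including crossovers. Controls who never use the device have no sessions, so these items cannot be compared between arms. Investigator guidance is stated only for the intervention group, so the plan should say how the same items are obtained for crossovers.
4. Daily minimum SpO2 with FiO2, ICU transfer and in-hospital death are tabulated by randomised arm and designated as safety outcomes.
5. The Design section, the risk paragraphs and the Assessment of Safety section are reconciled on which risks are known and on whether current use covers the indication under study.

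The cost is a few form fields, one survey question and one table. An investigator already guides the sessions, so no extra staff are needed.
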